7.3 Criteria for Delay of Trial Vaccine Administration and/or Blood Sampling

After enrollment, subjects may encounter clinical circumstances that warrant a delay in the administration of the trial vaccine. These situations are listed below. In the event that a subject meets a criterion for delay of trial vaccine administration, the subject may receive the trial

vaccine once the window for delay has passed as long as the subject is otherwise eligible for trial participation.

- Subjects with a clinically significant active infection (as assessed by the investigator).
- Subjects with a body temperature $\geq 38.0^{\circ}\text{C}$ ($>100.4^{\circ}\text{F}$), within 3 days of planned trial vaccine administration.
- Receipt or scheduled receipt of any other approved or authorized vaccines within 14 days (for all non-live vaccines or oral live vaccines) or 28 days (for parenteral live vaccines) before or after trial vaccine administration.
- Subjects who have been given antipyretics and/or analgesic medications within 24 hours prior to trial vaccine administration. The reason for their use (prophylaxis versus treatment) must be documented. Trial vaccine administration should be delayed to allow for a full 24 hours to have passed between having used antipyretics and/or analgesic medications and trial vaccine administration.

7.4 Criteria for Early Termination of a Subject's Trial Participation

Under some circumstances, a subject's trial participation may be terminated early. This means that no further trial procedures (including data collection) will be performed on that subject beyond the specific date of early termination of trial participation. The primary reason for early termination of the subject's trial participation should be documented using the following categories:

1. **Adverse Event:** The subject has experienced an AE (irrespective of being related/unrelated to the trial vaccine or trial-related procedures) that requires early termination because continued participation imposes an unacceptable risk to the subject's health and/or the subject's LAR is unwilling to allow the child to continue participation because of the AE. The primary reason for early termination of trial participation in this case will be withdrawal due to AE and not withdrawal of consent, see below.
2. **Lost to follow-up:** The subject did not return to the clinic and at least three documented attempts to contact the subject's LAR were unsuccessful.
3. **Withdrawal of consent:** The subject's LAR wishes to withdraw the child from the trial. The primary reason for early termination will be withdrawal of consent if withdrawal from participation is due to a non-medical reason (i.e., reason other than AE). While the subject's LAR has no obligation to provide a reason for withdrawing consent, attempts should be made to determine the underlying reason for the withdrawal and, where possible, the primary underlying reason should be documented.
4. **Premature trial termination by the sponsor, a regulatory agency, the IRB, or any other authority:** If the clinical trial is prematurely terminated by the sponsor, the investigator is to promptly inform the subject's LAR and the local IRB, and should assure appropriate follow

up for the subjects. The primary reason for early termination in this case will be trial termination.

5. Subject's death during trial participation.

6. Other.

For screen failure subjects, refer to Section 9.1.9.

7.5 Criteria for Premature Discontinuation of Trial Vaccine Administration

There are circumstances under which receipt of a further trial vaccine dose is a contraindication in this trial. These circumstances include anaphylaxis or severe hypersensitivity reactions after the first trial vaccine administration. If these reactions occur, the subject must not receive additional trial vaccine but the subject's LAR is encouraged to allow the child to continue participating in the trial for safety follow-up.

Early termination of a subject's trial participation will by default prevent the subject from receiving further doses of trial vaccine, as the subject will no longer be participating in the trial. In addition to criteria for early termination of a subject's participation (see Section 7.4), other situations may apply in which subjects may continue participating in the trial (e.g., contributing safety data according to the protocol) but trial vaccine administration is discontinued. Even if the subject is deemed ineligible to receive further doses of trial vaccine, all efforts should be made to continue the collection of safety data according to the protocol.

In addition, the primary reason for premature discontinuation of trial vaccine administration should be recorded in the electronic case report form (eCRF, end of trial vaccine administration page) using the following categories:

1. **Adverse Event:** The subject has experienced an AE (irrespective of being related/unrelated to the trial vaccine or trial-related procedures) for which subsequent trial vaccine administration(s) pose an unacceptable risk to the subject's health, but the subject will continue trial participation for safety, or a subset of other trial procedures.
2. **Lost to follow-up:** The subject did not return to the clinic and at least three documented attempts to contact the subject's LAR were unsuccessful.
3. **Withdrawal of consent:** The subject's LAR wishes the subject to withdraw from the trial. The primary reason for early termination will be withdrawal of consent if the subject withdraws from participation due to a non-medical reason (i.e., reason other than an AE). The reason for withdrawal, if provided, should be recorded in the eCRF.
4. **Premature trial termination by sponsor, a regulatory agency, the IRB, or any other authority.**

If the clinical trial is prematurely terminated by the sponsor, the investigator is to promptly inform the trial subject's LAR and local IRB and should assure appropriate follow up for the subjects. The primary reason for early termination in this case will be trial termination.

5. Subject's **death** prior to the next trial vaccine administration.
6. **Protocol deviation:** A protocol deviation is any change, divergence, or departure from the trial design or procedures of a trial protocol. The subject may remain in the trial unless continuation in the trial jeopardizes the subject's health, safety, or rights (see Section 7.4).
7. **Other.**

For criteria which also lead to early termination of a subject's trial participation, please refer to Section 7.4.

8.0 CLINICAL TRIAL MATERIAL MANAGEMENT

This section contains information regarding the investigational vaccine (HIL-214), placebo, and materials provided directly by the sponsor, and/or sourced by other means, that are required by the trial protocol, including important sections describing the management of clinical trial materials (CTM).

8.1 Trial Vaccine

Descriptions for the investigational vaccine and the placebo are provided in the following sections. In this protocol, because the trial is blinded, trial vaccine refers to the investigational vaccine (HIL-214) and placebo.

8.1.1 Investigational Vaccine

HIL-214 for injection is provided by HilleVax, Inc. in single dose 1 mL pre-filled syringes as a 0.65 mL volume (to deliver a 0.5 mL dose). HIL-214 contains 50 μ g GI.1/150 μ g GII.4c VLPs and 500 μ g of aluminum as Al(OH)₃.

The syringe contents may appear biphasic with a clear upper layer and a white precipitate. After mixing by shaking, a uniformly turbid suspension should be observed.

Each HIL-214 pre-filled syringe will be supplied in a tamper-evident, single dose carton.

8.1.2 Placebo

Placebo (0.9% NaCl [saline]) for injection is provided by HilleVax, Inc. in a container allowing delivery of a 0.5 mL dose. The placebo does not contain any preservatives.

The contents of the placebo container will appear clear and therefore, distinguishable from the vaccine.

Each placebo container will be supplied in a tamper-evident, single dose carton.

8.2 Labeling

A clinical label will be affixed to trial vaccine containers in accordance with local regulatory requirements. Trial vaccine identity (label text will state “HIL-214 or placebo”) will be included on the trial vaccine container label.

8.3 Inventory and Storage

Vaccines will be shipped in refrigerated, temperature-controlled containers with a temperature monitor. The trial vaccine must be stored, kept away from light, and maintained at a controlled temperature of 2°C to 8°C (36°F to 46°F), as specified on the label. The trial vaccine must be

CONFIDENTIAL

kept in an appropriate, limited access, secure place until it is used or returned to the sponsor or designee for destruction. The trial vaccine must not be frozen. Each kit is intended for single use only.

Receipt and dispensing of trial vaccine must be recorded by authorized personnel at the trial site. All sponsor-supplied investigational vaccine and placebo must be stored under the conditions specified on the label, and remain in the original container until dispensed. A daily temperature log of the vaccine storage area must be maintained. Temperature excursions must be reported to the sponsor as soon as possible and use of these vaccines requires sponsor approval. Temperature excursion information can be found in the pharmacy manual.

8.4 Dose and Regimen

The investigational vaccine 50 µg GI.1/ 150 µg GII.4c VLPs and 500 µg of aluminum as Al(OH)₃ or placebo will be administered as shown in Table 8.a.

Table 8.a Trial Vaccine Dose and Regimen for Trial NOR-109

Arm	Number of Subjects	Route of Administration	Regimen	
HIL-214*	14	IM (anterolateral thigh)	Day 1	Days 29-57
Placebo**	7			

Abbreviation: IM, intramuscular.

*50 µg GI.1/ 150 µg GII.4c VLPs and 500 µg of aluminum as Al(OH)₃.

**Placebo (0.9% NaCl [saline]).

8.5 Trial Vaccine Assignment and Dispensing Procedures

Trial vaccine assignment will be determined using a randomization code list generated by an independent statistician. This list will be stored in a secured area, accessible only to authorized unblinded trial personnel.

The investigational vaccine (HIL-214) and placebo are visually distinguishable and therefore, to maintain the blind, the trial vaccine doses (HIL-214 and placebo) will be prepared and administered by the unblinded personnel according to the instructions in the pharmacy manual.

The investigator or designee will be responsible for overseeing the administration of the trial vaccine to subjects enrolled in the trial according to the procedures stipulated in this trial protocol, but will not directly observe the administration of trial vaccine. The trial vaccine will be administered only by unblinded personnel who are qualified to perform that function under applicable laws and regulations for that specific trial.

Expired trial vaccines must not be administered.

8.6 Precautions to Be Observed When Administering the Trial Vaccine

Prior to trial vaccine administration (HIL-214 or placebo), a subject must be determined to be eligible to receive trial vaccine (Sections 7.1 and 7.2), and it must be clinically appropriate in the judgment of the investigator.

Prior to subsequent trial vaccine administration, site staff must determine if the subject is eligible to receive the trial vaccine by evaluating the criteria outlined in Sections 7.3, 7.4 and 7.5.

Standard vaccination practices are to be observed and care should be taken when administering a trial vaccine intramuscularly in the anterolateral thigh area. In addition, World Health Organization (WHO) recommendations to reduce anxiety and pain at the time of vaccination should be followed [27]. Before administration of the trial vaccine, the injection site must be disinfected with a skin disinfectant (e.g., 70% alcohol). Allow the skin to dry. Refer to the pharmacy manual for details on preparation and administration of trial vaccine.

As with all injectable vaccines, trained medical personnel and appropriate medical treatment should be readily available in case of anaphylactic reactions after trial vaccine administration. For example, epinephrine 1:1000, diphenhydramine, and/or other medications for treating anaphylaxis should be available.

8.7 Randomization Code Creation and Storage

Trial vaccine assignment will be generated by an independent statistician using block randomization. The randomization code list will be stored in a secured area, accessible only to authorized unblinded trial personnel.

When the investigator or designee determines that a subject is eligible to receive trial vaccine, the authorized unblinded trial personnel will randomize the subject to either the HIL-214 or placebo arm of the trial by selecting a randomization code from the ordered randomization code list, using a unique subject number assigned to the subject.

Subjects who are randomized but not dosed will be replaced.

8.8 Trial Vaccine Blind Maintenance

This is a randomized, double-blind trial. The subjects, data collectors (e.g., investigator) and data evaluators are blinded to the material administered. In this protocol, because the trial is blinded, trial vaccine refers to both the investigational vaccine (HIL-214) and placebo.

Trial vaccine administration must be done by designated unblinded site staff, in which the trial vaccine is selected using the subject's number (see Section 8.7). The designated unblinded site staff must not be involved with data collection of any sort including safety evaluation of the subject after administration of the trial vaccine.

8.9 Unblinding Procedure

The trial blind shall not be broken by the investigator unless information concerning HIL-214 is necessary for the medical treatment of a subject. In the event of a medical emergency, if possible, the medical monitor should be contacted before the trial blind is broken to discuss the need for unblinding. For unblinding a subject, the trial vaccine assignment will be obtained by an independent authorized unblinded individual who will have access to the randomization code list.

The sponsor's pharmacovigilance department must be notified as soon as possible if the trial blind is broken by the investigator and the completed SAE form, if applicable, must be sent within 24 hours. The date, time, and reason the trial blind is broken must be recorded in the source document and the same information (except the time) must be recorded on the electronic case report form (eCRF).

If any subject is unblinded, the subject must be withdrawn from the trial and their data no longer evaluated. Subjects should continue to be monitored for safety follow-up.

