13.1.1 Analysis Sets

Safety Set (SAF): The SAF will consist of all subjects who received at least one dose of HIL-214 or placebo. The SAF will be used as the primary population for analyses of safety data. The analyses using the SAF will be performed according to the trial vaccine actually administered at Visit 1.

Full-Analysis Set (FAS): The FAS will include all subjects who are randomized and received at least one dose of HIL-214 or placebo. The analyses using the FAS will be performed according to the trial vaccine that the subject was randomized to receive.

Per-Protocol Set (PPS): The PPS will include all subjects in the FAS who have no major protocol deviations. A major protocol deviation is defined as any change or departure from the trial design or procedures of a trial protocol, which affects evaluation of immunogenicity objectives. The categories of major protocol deviations include: (1) not meeting selected entry criteria, (2) receiving wrong or incomplete trial vaccine, (3) receiving prohibited therapies, and (4) other major protocol deviations. Prior to unblinding, all protocol deviations will be reviewed to determine the final list of deviations leading to the exclusions from the PPS.

The PPS will be used as primary population for analyses of immunogenicity data.

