13.1.4 Safety Analyses

All safety data analyses will be performed using the SAF. Summaries will be provided for each trial arm and overall.

Solicited AEs

Solicited AEs will be assessed during 30 minutes after administration of each dose of trial vaccine and then daily for 7 days (including the day of administration). For each solicited AE, the number and percentage of subjects will be computed, for each day from Day 1 to Day 7 after each trial vaccine dose administration (including the day of trial vaccine administration) and overall.

Solicited AEs will be summarized by intensity and, for systemic events, by relationship to the trial vaccine. For subjects with more than 1 episode of the same event within an interval, the maximum intensity and strongest relationship will be used for tabulations.

Body temperature measurements will be summarized in categories (including fever, defined as temperature $\geq 38^{\circ}\text{C}$), without adjustment for the route of measurement. Summaries of the day of first onset of each event and the number of days subjects experienced each event will also be provided.

Data from the 30 minutes assessment will be summarized separately.

Unsolicited AEs

Any unsolicited AEs, SAEs, MAAEs, and AEs leading to trial vaccine or trial withdrawal, will be coded using MedDRA, and summarized by system organ class (SOC) and preferred term (PT) using number and percentage of subject with an AE. Subjects with more than one occurrence for the term will be counted only once for this term.

For any unsolicited AEs, collected up to 28 days after administration of each dose of trial vaccine (including the day of administration), summaries will also be provided by event intensity (mild, moderate, severe) and relationship (not related, related) to trial vaccine or trial procedures. For subjects with more than one AE within a SOC or PT, then the AE with the maximum intensity or strongest relationship within each SOC and each PT will be included in the summaries by intensity or relationship, respectively.

Any unsolicited AEs will be summarized in the following 3 time intervals: 1) overall up to 28 days after trial vaccine administration, 2) with onset between 1 and 7 days after each dose

(including the day of trial vaccine administration), and 3) with onset between 8 and 29 days after each dose (including the day of trial vaccine administration).

AEs leading to trial vaccine withdrawal

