### 3.2. Study Endpoints

Endpoint	Summary Measures
Primary Endpoints	

Occurrence and severity of solicited local reactions up to 7 days after each dose of trial vaccine.

Occurrence, severity, and relationship of solicited systemic AEs up to 7 days after each dose of trial vaccine.

Occurrence, severity, and relationship of unsolicited AEs up to 28 days after each dose of trial vaccine.

Occurrence, severity, and relationship of AEs leading to withdrawal of trial vaccine up to 56 days post-dose 1.

	
Number of, and proportion of subjects with:
 

Solicited local reactions* up to 7 days post-dose 1 and dose 2.

Solicited systemic AEs** up to 7 days post-dose 1 and dose 2.

Unsolicited AEs up to 28 days post-dose 1 and dose 2.

AEs leading to withdrawal of trial vaccine up to 56 days post-dose 1.

 
In the safety set (SAF).

Secondary Safety Endpoints	

Occurrence, severity, and relationship of AEs leading to withdrawal from the trial, SAEs and MAAEs throughout the entire trial period

	

AEs leading to withdrawal from the trial, SAEs and MAAEs throughout the entire trial period.

 
In the SAF.

Secondary Immunogenicity Endpoints	
At baseline, pre-dose 2, 28 days post-dose 2 and 6 months post-dose 2: 

HBGA blocking antibody titers.

Pan-Ig antibody titers

	

Seroresponse Rate (SRR)*** for GI.1 titers pre-dose 2 and 28 days post-dose 2

SRR*** for GII.4 titers pre-dose 2 and 28 days post-dose 2.

GI.1 Geometric Mean Titers (GMTs) at baseline, pre-dose 2, 28 days post-dose 2 and 6 months post-dose 2.

	

• GII.4 GMTs at baseline, pre-dose 2, 28 days post-dose 2 and 6 months post-dose 2.

• GI.1 Geometric Mean Fold Rise (GMFR) from baseline to pre-dose 2, 28 days post-dose 2 and 6 months post-dose 2.

• GII.4 GMFR from baseline to pre-dose 2, 28 days post-dose 2 and 6 months post-dose 2.

 
In the per protocol set (PPS). Selected analyses may be provided using the full analysis set (FAS).

Exploratory Endpoints	

- [REDACTED]
- [REDACTED]

\* Injection site pain, erythema, induration, and swelling.  

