## 9. Safety Analysis

The purpose of this section is to define the safety parameters for the study and to summarise the safety results. All safety analyses will be conducted on the SAF. Safety measurements will include adverse events (AEs), serious AEs (SAEs), medically attended AEs (MAAEs), solicited AEs, physical examinations and vital signs measurements. Individual subject listings will be provided to support the tables. See section 3.2 for a list of the safety endpoints and summary measures.

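### The unblinding rule takes a subject's data out of evaluation, which contradicts the Safety Set and the whole-trial safety endpoints

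*Protocol*

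**What the plan says.** Protocol 8.9 allows a code break by the investigator only for clinical need: "The trial blind shall not be broken by the investigator unless information concerning HIL-214 is necessary for the medical treatment of a subject". It then sets the consequence: "If any subject is unblinded, the subject must be withdrawn from the trial and their data no longer evaluated". The next sentence adds: "Subjects should continue to be monitored for safety follow-up". SAP 4.2 repeats all three statements.

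The analysis text takes a different line. Protocol 13.1.1 and SAP 4.3.4 define the Safety Set in the same words: "The SAF will consist of all subjects who received at least one dose of HIL-214 or placebo". Neither makes an exception for unblinding. Protocol 13.1.4 states: "All safety data analyses will be performed using the SAF". SAP 9 agrees: "All safety analyses will be conducted on the SAF". Among the secondary safety endpoints, SAP 3.2 lists "SAEs and MAAEs throughout the entire trial period".

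Two other places bear on what happens to such an infant. Protocol 7.4 explains early termination of participation: "This means that no further trial procedures (including data collection) will be performed on that subject beyond the specific date of early termination". SAP 5.1 includes unblinding among the reasons for discontinuing the study.

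**The concern.** The unblinding rule refers to a subject's data without qualification, so as written it reaches safety data as well as antibody titers. The sentence on continued monitoring covers conduct. It does not say that what is observed enters the summaries. A programmer therefore has two instructions that cannot both be followed for an unblinded infant, and neither document ranks them.

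The primary objective is safety compared with placebo. A code break is permitted only when treating the infant depends on knowing the assignment, so the infants affected would be those with a medical problem. Omitting their later data would be selective, and it would lower the affected arm's event percentages if further events occurred.

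**Working it through.** The plan has no figure to reproduce. The sample size is descriptive (Protocol 13.3, SAP 4.1) and no unblinding rate is given. The check is a comparison of texts, followed by an illustration of scale.

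**Step 1. The texts side by side, for an infant who is dosed and later unblinded**

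| Question | Unblinding rule (Protocol 8.9, SAP 4.2) | Rest of the plan |
|---|---|---|
| Do the safety data count? | No longer evaluated, with no data type exempted | Yes: every dosed infant is in the SAF, and all safety analyses use it |
| Over what period? | Up to the code break, on a forward reading | SAEs and MAAEs to the end of the trial; unsolicited AEs for 28 days after each dose |
| Are data still collected? | Withdrawn, yet still monitored | Protocol 7.4 stops collection at early termination; Protocol 10.4.4 continues SAE collection to Visit 4 |
| Which rule wins? | Not stated | Not stated; SAP Section 11 records only the All Enrolled Set |

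**Step 2. Which events would be lost**

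The natural sense of the rule is forward-looking. The event that prompted the code break has already been counted and stays. SAEs, MAAEs and unsolicited AEs after the break are exposed. Each subject counts once at each level of a table (SAP 9.2, 9.2.3). If the trigger was an SAE, a later SAE therefore leaves the any-SAE row unchanged and affects only a new system organ class or preferred term row. If the trigger was another type of event, the any-SAE row can change too.

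**Step 3. Effect on one table row**

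Inputs: 14 HIL-214 and 7 placebo infants (SAP 4.1). Percentages for unsolicited AEs and SAEs are out of the number of subjects in the SAF (SAP 9.2, 9.2.3), so the infant stays in the denominator. Assumption: one infant is unblinded and later has the arm's only event in some preferred term.

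- HIL-214: 1/14 = 7.1% if the event is included, 0/14 = 0% if it is omitted.
- Placebo: 1/7 = 14.3% if the event is included, 0/7 = 0% if it is omitted.

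**Step 4. How much of that infant's observation is exposed**

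Dose 2 falls 28 to 56 days after dose 1, and Visit 4 falls 180 days after dose 2. Nominal follow-up is 28 + 180 = 208 to 56 + 180 = 236 days, ignoring the ±10-day window at Visit 4. The code-break times below are assumptions.

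- Break 7 days after dose 1: (208 − 7)/208 = 201/208 = 96.6%, or (236 − 7)/236 = 229/236 = 97.0%. Of the primary unsolicited-AE window after dose 1, (28 − 7)/28 = 75% falls after the break.
- Break 28 days after dose 2: 180 − 28 = 152 days remain, which is 152/208 = 73.1% or 152/236 = 64.4%.

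These are shares of one infant's follow-up. No planned summary uses person-time, so they show only how much of the observation period depends on the unresolved rule.

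**The case against.** The best defence is that the plan's analysis text already includes these infants. The SAF admits every dosed subject, all safety analyses run on it, and SAEs and MAAEs are summarised for the overall trial period. The unblinding rule appears only in the sections on blinding, and no analysis-set definition, derivation or table specification carries it out. A reader might infer from the rule that nothing provides for analysing an unblinded infant's safety data. That goes too far, because the general SAF text does provide for it. What is missing is a statement of which text governs. This limits the point but does not remove it: a rule written for unblinded subjects can reasonably be taken to override a general one, and SAP 4.2 repeats it without reconciling the two.

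It can also be said that the outcome-linked event is the trigger, and that a forward reading keeps it. This is correct and reduces the likely effect. What remains exposed is the later course of infants selected because they had a medical problem.

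Finally, unblinding may never occur, the trial is descriptive, SAE collection runs to Visit 4 (Protocol 10.4.4) and all AEs are listed (SAP 9.2). This also stands, and it confines the risk to the by-arm summary tables. Those tables are nevertheless the planned presentation of the primary and secondary safety endpoints. With arms of 14 and 7, a single infant is visible in them.

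**Conclusion.** The contradiction is certain; its effect depends on a code break happening. The rule as written conflicts with the SAF definition, with the use of the SAF for all safety analyses, and with the whole-trial SAE and MAAE endpoints. If applied, it would omit safety data from infants selected by medical need. For one unblinded infant with one later event in a new preferred term, the row changes by 7.1 percentage points on HIL-214 or 14.3 on placebo. This assumes the forward reading and the planned arm sizes.

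A reader might infer a stronger version: that everything the infant contributed is removed, including the triggering event, so that 1/14 becomes 0/13 or 1/7 becomes 0/6. The documents do not support it. The wording points forward, and nothing in either document takes a dosed infant out of the SAF denominator. Nor do they support a claim that the events would go unreported, since SAE reporting and the AE listings continue. The point is worth fixing because it touches the primary objective and the remedy is a short text change.

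**What to change.** In SAP 4.2 now, recorded in SAP Section 11, and in Protocol 8.9 at the next amendment, replace the clause that ends evaluation of the subject's data with text such as:

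> Unblinded subjects remain in the SAF (by vaccine received at Visit 1) and the FAS (as randomized). All safety data collected before and after unblinding are included in the safety summaries, with post-unblinding assessments flagged in listings. Any exclusion is limited to the PPS, through the planned deviation review.

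In the same protocol amendment, state that unblinding stops further trial vaccine but that safety follow-up and data collection continue through Visit 4 unless the legally acceptable representative withdraws consent. Protocol 7.5 already provides this status: vaccine stopped, safety data still collected. The statement also removes the tension with Protocol 7.4.

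Leave unblinding among the SAP 5.1 discontinuation reasons until that amendment. Moving it to the second-dose withdrawal reasons would not work: it could not capture a code break after dose 2, and unblinding is not among the Protocol 7.5 categories.

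The cost is a short text replacement in each document, one line in SAP Section 11 and one added statement in the protocol. The SAP can settle the analysis at once; the change in conduct has to wait for the amendment. The downside is that some safety assessments made with knowledge of the assignment are kept. Flagging makes them visible.
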